6.4.2 Classification of participants as analgesic, antihistamine users

If a participant has taken a new analgesic/increased regimen of analgesic, or taken an antihistamine, on 1 or more days (need not be consecutive) in a study period (Initial Treatment Period or Maintenance Treatment Period), then for that period the participant will be classified as an analgesic or antihistamine user, respectively. The period under consideration is to match the period as defined for the HSSDD for the Initial Treatment Period or HSSQ for the Maintenance Treatment Period, based on dates/times of the medications taken.

New analgesic/increased regimen of analgesic use, regardless of indication, is defined as an analgesic medication with start date on or after the first dose of study medication. Stable

analgesics (ie, analgesics which were taken already before randomization) will not be included in this category of analgesic user. This classification will be used for selected subgroup analyses.

Antihistamine use is identified by considering the ATC classification. This classification is used for analyzing the Worst Itch endpoint and for selected subgroup analyses, by visit, for the Initial Treatment Period and Maintenance Period as applicable.

Additionally, if a participant has taken a new analgesic/increased regimen of analgesic on 1 or more days (need not be consecutive) prior to the Week 16 visit, then for that week the participant will be classified as an analgesic user. This classification will be used to adjust the formal analysis of the Worst Skin Pain secondary endpoints. If there is a visit date but no HSSDD available at the visit, then the analgesic/antihistamine user status for that week will be derived based on the visit date. If there is no visit available, then the weekly analgesic/antihistamine user status will default to the analgesic/antihistamine status for the overall study period.

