4 STATISTICAL/ANALYTICAL ISSUES

4.1 Adjustments for covariates

The primary efficacy analyses and selected secondary analyses will be adjusted for the 2 randomization stratification variables:

- Hurley Stage at Baseline (II or III)
- Baseline antibiotic use (Yes or No)

If a participant is stratified in the incorrect stratum (ie, the stratum recorded in the Interactive voice or web Response System differs from the actual stratum the participant belongs to), the actual stratum will be used for the analysis.

The continuous secondary endpoints will also include the Baseline value as a covariate.

The Worst Skin Pain secondary endpoints (change from Baseline continuous endpoint and pain response binary endpoint) will also include analgesic use as a covariate.

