Change from Baseline in worst skin pain score will be presented by treatment group. The analysis model will be based on an ANCOVA with fixed effects of treatment, Hurley Stage at Baseline, Baseline antibiotic use, analgesic use (Section 6.4.2) and Baseline value as a covariate.

The LSM, SE, and 95% CI for the LSM will be presented by treatment group. For the comparison between placebo and bimekizumab, the difference between the LSM, the associated 97.5% CI for the contrasts, and the corresponding p-value will be presented. If one dose regimen is tested at the 0.05 significance level as determined in Section 4.5, then the confidence interval will be 95% instead of 97.5% for that dose with a corresponding $Z_{\alpha/2}$ of 1.96.

8.3.4.2 Sensitivity analysis of change from Baseline in skin pain score at Week 16

A sensitivity analysis using the same analysis model as in Section 8.3.4.1 will be used, based on observed data. Estimand and intercurrent event details are specified in Table 8–2.

8.3.5 HSSDD skin pain response at Week 16

The analysis set for the analyses of the skin pain response will be restricted to those study participants in the RS with a Baseline worst skin pain score of 3 or higher. The weekly scores and Baseline score are derived as specified in Section 8.3.4.

8.3.5.1 Primary analysis of skin pain response at Week 16

Skin pain response at Week 16, as assessed by the “worst skin pain” item in the HSSDD, is defined as an improvement in the weekly worst skin pain score of at least 3 points versus Baseline.

The primary analysis will be based on a logistic regression model including a fixed effect for treatment, Hurley stage at Baseline, Baseline antibiotic use, and analgesic use (Section 6.4.2).

The odds ratio versus placebo, p-value (from Wald test), and 97.5% CI will be calculated. If one dose regimen is tested at the 0.05 significance level as determined in Section 4.5, then the confidence interval will be 95% instead of 97.5% for that dose. Missing data will be handled as specified in Section 4.2.1.2. Estimand and intercurrent event details are specified in Table 8–2.

The number and percentage of participants who are pain responders at Week 16 will be summarized by treatment group.

By-participant listings of pain response status will be provided.

8.3.5.2 Sensitivity analyses of Skin Pain Response at Week 16

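### Both confirmatory Worst Skin Pain analyses adjust for analgesic use that starts after first dose, so the contrast tested is not the treatment effect that Table 8-2 targets

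*SAP*

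**What the plan says.** Section 4.1 sets the covariates: "The Worst Skin Pain secondary endpoints (change from Baseline continuous endpoint and pain response binary endpoint) will also include analgesic use as a covariate".

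Section 6.4.2 defines the variable. New or increased use, whatever the indication, "is defined as an analgesic medication with start date on or after the first dose of study medication". Stable treatment is left out: "analgesics which were taken already before randomization) will not be included in this category of analgesic user". For the formal analyses a participant counts as a user "if a participant has taken a new analgesic/increased regimen of analgesic on 1 or more days (need not be consecutive) prior to the Week 16" (the cut-off is the Week 16 visit). The same sentence then assigns the status to a single week, and later sentences speak of a weekly status. The window is thus either the whole span from first dose to Week 16 or one week before that visit. Section 6.4.2 closes the matter of purpose: "This classification will be used to adjust the formal analysis of the Worst Skin Pain secondary endpoints".

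The models follow. The ANCOVA in 8.3.4.1 includes "Baseline antibiotic use, analgesic use (Section 6.4.2) and Baseline value as a covariate". The logistic model in 8.3.5.1 includes "Baseline antibiotic use, and analgesic use (Section 6.4.2").

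Section 4.5 puts both endpoints in the multiplicity-controlled sequence, analysed by the Section 8.3 methods. Significance at Step 6 (pain response) for one dose lets the other dose be retested at 0.05. Section 3.9 and Table 8-2 list two intercurrent events: systemic antibiotic rescue, and treatment discontinuation due to an AE or lack of efficacy. Analgesic use is in neither place.

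**The concern.** Every other covariate in these two models is fixed before treatment. This one is not. A participant whose pain does not improve may start an analgesic, so use can follow from treatment through pain. Use and pain can also share causes that nobody measured. Holding such a variable fixed gives up the protection of randomisation: the treatment coefficient compares users with users and non-users with non-users, and treatment may have altered who falls in each group.

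Table 8-2 targets the difference in mean change under a hypothetical strategy, and the odds ratio for response under a composite strategy. Both strategies cover only the two listed events, so new analgesic use is part of the course of pain being compared. Table 8-2 also describes the response model as the one used for the primary analysis, and that model (8.2.2) has no analgesic term.

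At stake are Steps 5 and 6 for both doses, the release of alpha after Step 6, and the endpoint that Section 2.4 names as driving the sample size. The sensitivity analyses in 8.3.4.2 and 8.3.5.2 keep the same models, so they would not expose a distortion.

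**Working it through.** **1. The plan's power.** Inputs from Table 2-1, change from Baseline: -2.0 (SD 3.2, N=140) against -0.5 (SD 3.7, N=70), a difference of 1.5.

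SE = √(3.2²/140 + 3.7²/70) = √(0.0731 + 0.1956) = 0.518. Noncentrality = 1.5/0.518 = 2.89, Satterthwaite df about 122.

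| Comparison | Two-sided alpha | Recomputed | Stated |
|---|---|---|---|
| 140:70 | 0.025 | 0.733 | 0.73 |
| 140:70 | 0.05 | 0.819 | 0.81 |
| 280:70 (difference 1.7, SE 0.482) | 0.025 | 0.893 | 0.89 |

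For pain response, two proportions with continuity correction give 0.513 and 0.631 for 104:52 (stated 0.53 and 0.65) and 0.954 for 208:52 (stated 0.95). The stated powers are therefore those of unadjusted comparisons.

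**2. What the term does to the linear contrast.** Leaving other covariates aside, least squares gives

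adjusted = unadjusted - γ × (use on bimekizumab - use on placebo),

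where γ is the fitted user-minus-non-user difference in pain change. If bimekizumab lowers use, the bracket is negative. A positive γ (users have worse pain) moves the contrast toward zero. A negative γ (analgesics mainly relieve pain) moves it away. Equal use leaves it unchanged.

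**3. Size under assumptions.** The SAP gives no user shares and no link between use and pain, so these are assumed. Large-sample simulation, true total difference -1.5, common SD 3.4 (the pooled value is √((139 × 3.2² + 69 × 3.7²)/208) = 3.37), power for 140:70 at 0.025:

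| Use, bimekizumab vs placebo | Correlation of use with worse pain | Analgesic effect (points) | Unadjusted | Adjusted | γ implied | Power, unadjusted → adjusted |
|---|---|---|---|---|---|---|
| 15% vs 30% | 0.5 | 0 | -1.511 | -1.068 | 0.443/0.15 = 2.95 | 0.79 → 0.51 |
| 15% vs 30% | 0.5 | -1 | -1.505 | -1.214 | 0.291/0.15 = 1.94 | 0.81 → 0.63 |
| 15% vs 30% | 0 | -1 | -1.485 | -1.640 | -0.155/0.15 = -1.03 | 0.77 → 0.84 |
| 10% vs 30% | 0.5 | 0 | -1.501 | -0.913 | 0.588/0.20 = 2.94 | 0.78 → 0.36 |
| 10% vs 30% | 0 | -1 | -1.491 | -1.693 | -0.202/0.20 = -1.01 | 0.77 → 0.86 |
| 25% vs 30% | 0.5 | 0 | -1.495 | -1.355 | 0.140/0.05 = 2.80 | 0.78 → 0.75 |
| 25% vs 30% | 0 | -1 | -1.514 | -1.568 | -0.054/0.05 = -1.08 | 0.78 → 0.82 |
| 30% vs 30% | 0.5 | 0 | -1.505 | -1.504 | not determined | 0.78 → 0.85 |

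The unadjusted power here, about 0.78, comes from the common SD. It is not the plan's 73%, so read the power column only as a change within a row.

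**4. No total effect.** If treatment changes neither pain nor use, the adjusted contrast is 0 and the error rate is kept. If the total effect on pain is 0 but use is 15% vs 30% (correlation 0.5, analgesic effect -1), the adjusted contrast is +0.28.

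**5. Pain response.** Table 2-1 gives 0.43 vs 0.23, an odds ratio of (0.43/0.57)/(0.23/0.77) = 2.53. Adjusted for use with correlation 0.3 to 0.5, it is 2.28 to 2.18 at 15% vs 30% and 2.19 to 2.03 at 10% vs 30%. With equal use it rises to 2.59 to 2.76, because odds ratios change on conditioning even without bias. These runs gave the analgesic no effect of its own, so they show only one direction.

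**The case against.** The strongest defence is the aim. A pain score recorded under a new analgesic partly reflects that analgesic, and more rescue use on placebo could hide a drug effect. The aim is reasonable. A covariate term does not achieve it, however, unless nothing unmeasured drives both use and pain, and participants in more pain are the likeliest to start an analgesic.

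The link may also be weak. Use counts for any indication and on as little as one day, and a one-week window would give fewer users than the whole period. If use hardly differs between arms, the distortion is small, and the term may even add precision (last row of the table). This stands, and it limits the claim about size. The variable remains post-randomisation under either window.

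Three stronger readings are tempting. A reader might infer that the adjustment must remove part of the drug's benefit. The SAP gives no rates from which that follows, and the contrast can move away from zero. A reader might infer an inflated type I error. It is kept when treatment changes neither pain nor analgesic use. A reader might infer that the stated power is wrong. It reproduces for an unadjusted test. It is simply not assured for the model that will be run.

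**Conclusion.** The point holds as a defect of specification. Two alpha-controlled tests condition on a variable that treatment can plausibly change and that the estimand does not mention, and no planned skin-pain sensitivity analysis omits it. The size is unknown. Around a true -1.5 points, the adjusted contrast lies between about -1.07 and -1.64 at 15% vs 30% use and between about -0.9 and -1.7 at 10% vs 30%. It is unchanged if use is equal. These figures rest on assumed use shares, a correlation with worse pain of 0 to 0.5, and an analgesic effect of 0 or -1 point. The primary endpoint and Steps 2 to 4 are not affected. The term should be changed before unblinding, because a confirmatory result should not depend on how treatment happens to shift analgesic use.

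**What to change.** Remove post-baseline analgesic use from the models in Sections 4.1, 8.3.4.1 and 8.3.5.1. If an analgesic term is wanted, replace it with analgesic use before first dose (yes/no), which can be derived from the prior medications already recorded (Section 6.4). The sensitivity analyses in 8.3.4.2 and 8.3.5.2 then follow without further edits.

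Removing the term alone would leave new analgesic use without a stated strategy. Add to Table 8-2 that pain scores are used regardless of new or increased analgesics (treatment policy). Keep the post-baseline classification for the descriptive tables in Sections 4.8 and 8.4.12, or for an analysis labelled supportive, and settle in 6.4.2 whether its window is one week or the whole period.

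The cost is SAP wording and at most one derived variable. No new data are needed, and the sample size stays as it is, because the stated power already belongs to an unadjusted comparison.

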7 MEASUREMENTS OF TREATMENT COMPLIANCE

Due to the method of administration of the treatments, compliance will be examined in terms of completed injections.

Treatment compliance will be calculated as:

$$\frac{N_{actual}}{N_{expected}} \times 100\%$$

where N_{actual} is the total number of actual (completed) injections, and $N_{expected}$ is the total number of expected injections. In this study, dosing occurs [REDACTED] from Week 0 to Week 46, where 2 injections are administered at each given visit either with active dosing or placebo injection. It is expected that a participant should complete a total of 48 injections by the end of study. If a participant discontinues early, then the number of expected injections is based on the time of early discontinuation relative to the dosing visits. For example, if a participant discontinues after Week 8 visit and prior to Week 10 visit, the total number of expected injections will be 10.

A summary of percent treatment compliance categorized as <75% and ≥75% will be provided by treatment group for each study period (Initial Treatment Period for the RS, Maintenance Treatment Period for the MS, and the combined Initial and Maintenance Treatment Period for the AMS).

A by-participant listing of treatment compliance will be provided.

8 EFFICACY ANALYSES

All efficacy analyses of primary, secondary, and other variables will be performed on the RS unless otherwise specified. All efficacy summary tables will be displayed by treatment sequence unless otherwise specified. The primary and secondary endpoints, and their components, will also be summarized by the derived Hurley Stage at Baseline (grouping each stage and overall) and treatment sequence and by the derived Baseline antibiotic use (yes/no and overall) and treatment group.

8.1 Lesion count assessment

The primary efficacy endpoint and some of the secondary and other efficacy endpoints discussed in Section 8.3 and Section 8.4 are based on the assessment and/or counts of different types of lesions in the following main anatomical regions at each visit.

- Inguinal (groin)
- Axillary (armpit)
- Chest/breast
- Gluteal
- Abdomen including supra pubic
- Back
- Head
- Neck
- Leg
- Other

These anatomical regions are further classified into the following locations, for the left and right sides of the body, as applicable:

- Inguinal excluding genital and pubic area
- Inguinal including genital and pubic area
- Submammary
- Intermammary
- Chest
- Breast
- Gluteal – Buttocks
- Gluteal – Perianal/Perineal
- Scalp
- Face

All “Other” anatomical regions with lesions present will be specified in free text on the eCRF.

The number of each of the following types of lesions will be recorded in each anatomical region, and then summed across all anatomical regions:

- Abscesses
- Inflammatory nodules
- Non-inflammatory nodules
- Draining tunnels (fistulas/sinus tracts)

- Non-draining tunnels (fistulas/sinus tracts)
- HS scars

If participants undergo lesion interventions as specified in the study protocol, the affected lesions will be counted by the Investigator as permanently present, thus accounting for potential bias due to the intervention. Section 8.4.23 specifies how the intervention data will be presented.

8.2 Primary efficacy endpoint

The primary and sensitivity analyses of HiSCR₅₀ response at Week 16 are summarized in Table 8–1.

Table 8–1: Estimand Details and Attributes for Primary Endpoint

Objective Clinical Category	Statistical Category (Section)	Estimands for Primary Endpoint			PLS (Analysis)
		Variable/Endpoint	Pop	IES	
Primary Objective: To evaluate the efficacy of bimekizumab in study participants with moderate to severe HS					
HiSCR ₅₀	Primary (Section 8.2.2)	HiSCR ₅₀ response at Week 16	RS	The main intercurrent events are receipt of systemic antibiotic rescue medication or discontinuation of study treatment due to an AE or lack of efficacy prior to Week 16. A composite strategy will be used, ie, the occurrence of an intercurrent event will be handled by evaluating the corresponding participants as treatment failures (nonresponders).	The odds ratio versus placebo based on a logistic regression. Missing values will be imputed using MI – MCMC/Monotone Regression under a missing at random assumption.

Table 8–1: Estimand Details and Attributes for Primary Endpoint

Objective Clinical Category	Statistical Category (Section)	Estimands for Primary Endpoint			PLS (Analysis)
		Variable/Endpoint	Pop	IES	
HiSCR ₅₀	Sensitivity (Section 8.2.3.1)	HiSCR ₅₀ response at Week 16	RS	Composite strategy , as for the primary analysis where the occurrence of an intercurrent event will be handled by evaluating the corresponding participants as nonresponders.	The odds ratio versus placebo based on a logistic regression. Missing values for any other reason will also be imputed as nonresponders.
HiSCR ₅₀	Sensitivity (Section 8.2.3.2)	HiSCR ₅₀ response at Week 16	RS	Composite strategy , as for the primary analysis.	The odds ratio versus placebo based on a logistic regression. Missing values will be imputed using MI – Reference-Based Regression under a missing not at random assumption.

Table 8–1: Estimand Details and Attributes for Primary Endpoint

Objective Clinical Category	Statistical Category (Section)	Estimands for Primary Endpoint			PLS (Analysis)
		Variable/Endpoint	Pop	IES	
HiSCR ₅₀	Sensitivity (Section 8.2.3.3)	HiSCR ₅₀ response at Week 16	RS	Composite strategy^a , as for the primary analysis.	A tipping point analysis will be used where various delta adjustments will be made to the assumed responses on the monotone missing data in each treatment group independently with various degrees of plausibility. The odds ratio versus placebo is based on a logistic regression for each value of delta.
HiSCR ₅₀	Sensitivity (Section 8.2.3.4)	HiSCR ₅₀ response at Week 16	RS	The main intercurrent events are receipt of systemic antibiotic rescue medication or discontinuation of study treatment due to an AE or lack of efficacy prior to Week 16. The intercurrent events will be handled using a treatment policy strategy , whereby the data from the Initial Treatment Period are used regardless of whether the intercurrent event occurred.	The odds ratio versus placebo is based on a logistic regression, as for the primary analysis.

Table 8–1: Estimand Details and Attributes for Primary Endpoint

Objective Clinical Category	Statistical Category (Section)	Estimands for Primary Endpoint			PLS (Analysis)
		Variable/Endpoint	Pop	IES	
HiSCR ₅₀	Sensitivity (Section 8.2.3.5)	HiSCR ₅₀ response at Week 16	RS	The main intercurrent events are receipt of systemic antibiotic rescue medication or discontinuation of study treatment due to an AE or lack of efficacy prior to Week 16. The intercurrent events will be handled using a while on treatment strategy , whereby only participants with a lesion count assessment at Week 16 who have not had an intercurrent event on or before Week 16 are included.	The odds ratio versus placebo is based on a logistic regression. Missing values will not be imputed.
HiSCR ₅₀	Sensitivity (Section 8.2.3.6)	HiSCR ₅₀ response at Week 16	FAS	Composite strategy , as for the primary analysis.	The odds ratio versus placebo is based on a logistic regression, as for the primary analysis.
HiSCR ₅₀	Sensitivity (Section 8.2.3.7)	HiSCR ₅₀ response at Week 16	PPS	Composite strategy , as for the primary analysis.	The odds ratio versus placebo is based on a logistic regression, as for the primary analysis.
HiSCR ₅₀	Sensitivity (Section 8.2.3.8)	HiSCR ₅₀ response at Week 16	CFS	Composite strategy , as for the primary analysis.	The odds ratio versus placebo is based on a logistic regression, as for the primary analysis.

Table 8–1: Estimand Details and Attributes for Primary Endpoint

Objective Clinical Category	Statistical Category (Section)	Estimands for Primary Endpoint			PLS (Analysis)
		Variable/Endpoint	Pop	IES	
HiSCR ₅₀	Sensitivity (Section 8.2.3.9)	HiSCR ₅₀ response at Week 16	RS	The same two intercurrent events used for the primary analysis will be used. Any missing data due to COVID-19 will also be considered an intercurrent event. A composite strategy will be used, ie, the occurrence of an intercurrent event will be handled by evaluating the corresponding participants as treatment failures (nonresponders).	The odds ratio versus placebo is based on a logistic regression, as for the primary analysis.
HiSCR ₅₀	Sensitivity (Section 8.2.3.10)	HiSCR ₅₀ response at Week 16	RS	Composite strategy , as for the primary analysis.	The odds ratio versus placebo based on a stratified Cochran-Mantel-Haenszel (CMH) test. Missing values not preceded by an intercurrent event will be imputed using MI – MCMC/Monotone Regression under a missing at random assumption.

CFS=Covid-19 Free Set; CMH=Cochran-Mantel-Haenszel; COVID-19=coronavirus disease 2019; FAS=Full Analysis Set; HiSCR=Hidradenitis Suppurativa Clinical Response; IES=intercurrent event(s) strategy; MCMC=Markov Chain Monte Carlo; MI= multiple imputation; PLS=Population-level summary; Pop=Population; PPS=Per-Protocol Set; RS=Randomized Set

^a The composite estimand strategy will be modified in the tipping point analysis such that participants with intercurrent events will be treated as nonresponders only in the bimekizumab treatment groups.

8.2.1 Derivation of HiSCR₅₀ at Week 16

The following algorithm will be applied to derive HiSCR₅₀ at each visit, based on total lesion counts across anatomical regions for the 3 relevant lesion types recorded as specified above in Section 8.1:

1. Calculate the AN count at each visit as the total number of abscesses plus the total number of inflammatory nodules, across all anatomical regions
2. Calculate the percentage change from Baseline in AN count (% Δ AN) at each visit as

$$100 \times (\text{AN count at post-Baseline visit minus Baseline AN count}) / (\text{Baseline AN count})$$

3. Calculate the change from Baseline in the abscess count by subtracting the Baseline abscess count from the abscess count at each post-Baseline visit
4. Calculate the change from Baseline in the draining tunnel (fistula/sinus tract) count by subtracting the Baseline draining tunnel (fistula/sinus tract) count from the draining tunnel (fistula/sinus tract) count at each post-Baseline visit
5. If the % Δ AN is less than or equal to -50%, and the change from Baseline in the abscess count is zero or negative (ie, non-positive) together with a non-positive change from Baseline in the draining tunnel (fistula/sinus tract) count, then the HiSCR₅₀ will be assigned a value of 1 (ie, HiSCR₅₀ is achieved); otherwise, the HiSCR₅₀ will be assigned a value of 0 (ie, HiSCR₅₀ is not achieved).

In cases where the inflammatory nodule, abscess or draining tunnel (fistula/sinus tract) count is missing and will not allow for the HiSCR₅₀ calculation, the rules for handling missing values in the analysis will be applied (Section 4.2.1 and Section 8.2.3).

The primary efficacy endpoint is attained if the participant has a HiSCR₅₀ of 1 at Week 16.

